Following the occurrence of fatal serious AEs (SAEs) in Study ATX-MTM-002, the Sponsor, in consultation with the DMC and external experts, evaluated the data and reassessed the benefit/risk profiles of the 1.0×10^{14} vg/kg and 3.0×10^{14} vg/kg dose levels. As of the data cutoff date of 08 July 2020, 5 subjects who received 3.0×10^{14} vg/kg AT132 developed AT132-related SAEs involving the hepatobiliary system. In 2 subjects, these SAEs resolved; in 3 subjects, fatal events occurred subsequent to severe cholestatic liver dysfunction. Within the 3.0×10^{14} vg/kg dose level cohort, 8 of 17 subjects (47.1%) experienced 26 SAEs considered related to AT132. In contrast, within the 6 subjects dosed at the 1.0×10^{14} vg/kg dose level, all of whom are ≥ 2 years from AT132 administration, 1 (16.7%) subject experienced 4 AT132-related SAEs, all resolved, and none involved the hepatobiliary system. In addition to a favorable safety profile observed in the subjects treated with 1.0×10^{14} vg/kg, a clinically meaningful benefit continues to be observed in this group at last follow-up. In this group, which had a mean 20.5 hours (SE 2.02) of ventilation per day at baseline ($n = 5$ [83.3%] with invasive ventilation; $n = 1$ [16.7%] with non-invasive ventilation), 5 out of 6 (83.3%) subjects were ventilatory independent at last follow-up (as of data cutoff date 08 July 2020). With respect to gross motor development, at baseline 5 of the 6 subjects did not perform any of the following major motor milestones: sit unassisted for 30 seconds, raise self to standing position, stand alone, or walk alone. At baseline, 1 subject did sit unassisted for 30 seconds but did not perform the remaining motor tasks. At last follow-up following AT132 administration at 1.0×10^{14} vg/kg, 5 out of 6 subjects performed all of these motor tasks, including walking alone. Regarding performance on the Children's Hospital of Philadelphia Infant Test of Neuromuscular Disorders (CHOP INTEND), this 1.0×10^{14} vg/kg group demonstrated a baseline mean score of 37.7 (SE 2.42). At last follow-up, performance had improved to a mean score of 56.5 (3.97).

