5.1.1.11.2 Assessment of Time Off Ventilator

5.1.1.11.2.1 Daily Ventilator Dependence Diary

For subjects in Part 1 who have not completed the Week 24 visit and for subjects in Part 2 (including any subjects enrolled under protocol v5 and beyond), an electronic diary will be completed by the parent/LAR/caregiver to collect the type of ventilatory support and the amount of time the subject spent off of ventilatory support in a 24-hour period. The diary should be completed daily by the same parent/LAR/caregiver (whenever possible). Site staff should set up the electronic diary prior to distribution to the parent/LAR/caregiver and review the training with the parent/LAR/caregiver. The daily diary collection will begin after informed consent (or re-consent to protocol v5 or later for Part 1 subjects) and continue through Week 48. However, if after the Week 24 visit, ventilator support has been discontinued, the daily diary will no longer need to be completed. If ventilator support is resumed, the daily diary completion will resume through Week 48 or discontinuation of the ventilatory support, whichever occurs first. For

subjects in Part 1 who have already completed the Week 24 visit, a daily diary will not be completed.

5.1.1.11.2.2 Ventilator Dependence Questionnaire

A questionnaire will be completed by the parent/LAR/caregiver to collect the type of ventilatory support and the amount of time the subject spent off of ventilatory support in a 24-hour period at clinic and contact visits ([Appendix 4](#)).

For subjects in Part 1 who have already completed the Week 24 visit, the parent/LAR/caregiver will complete the ventilator dependence questionnaire at clinic and contact visits through Month 120.

For subjects in Part 1 who have not completed the Week 24 visit and for subjects in Part 2 (including any subjects enrolled under protocol v5 and beyond), the daily diary will be completed per [Section 5.1.1.11.2.1](#). After the daily diary has been stopped or the subject has completed Week 48, the parent/LAR/caregiver will complete the ventilator dependence questionnaire at clinic and contact visits through Month 120.

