4.4.2.2 Main Analytical Approach

The secondary efficacy analyses will be conducted for the FAS.

4.4.2.2.1 Time to reduction in required ventilator support to ≤ 16 hours a day (only in participants who require invasive ventilation) at Week 24

This endpoint will be summarized for low dose and the high dose groups separately in the participants who require invasive ventilation. Kaplan-Meier plots along with median (95% CI) time from the study start date to event will be provided.

The number of hours of ventilator support at each collected time point for this analysis will be taken directly from the daily diary (Protocol V5.0 and later) or by assessment of time off ventilator questionnaire (prior to Protocol V5.0). The first instance of time reduction reported as ≤ 16 hours per day will be considered an event. Participants will be censored at either Week 24 or withdrawal from study, whichever occurs first.

4.4.2.2.2 Change from baseline in Children's Hospital of Philadelphia Infant Test of Neuromuscular Disorders (CHOP INTEND) at Week 24

The change from baseline will be analyzed using the MMRM in a similar method to that used for the primary analysis of the primary efficacy endpoint, described in [Section 4.3.2](#).

Estimated change from baseline in CHOP INTEND score at Week 24 will be summarized by dose level.

In addition, the CHOP INTEND score and corresponding change from baseline at each visit will be summarized descriptively by dose level group.

The CHOP INTEND is an assessment scale that was originally designed to quantify motor abilities in infants aged 1.4 to 37.9 months, with spinal muscular atrophy type I (SMA-I) ([Glanzman, 2010](#)) and has been validated for XLMTM ([Duong, 2021](#)). The scale contains 16 questions, each of which is scored on a scale of 0 to 4, with 0 being no response/ability to perform the movement and 4 highest ability to perform the task, per CHOP INTEND item instructions.

The score used for analysis is the total sum of all 16 questions, which will range from 0 to 64. Higher score indicates better neuromuscular function. If an item is missing or scored as "Could Not Test (CNT)" then 0 will be imputed for the item score.

If a participant has 2 assessments with a total score of ≥ 56 , the CHOP INTEND will not be required for future visits.

Subject line plots of the CHOP INTEND over time will be created.

4.4.2.2.3 Change from baseline in maximal inspiratory pressure (MIP) at Week 24

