4.4.2.2.8 Survival

This endpoint will be summarized for low dose and the high dose groups separately for all participants in the FAS. Kaplan-Meier plots of time from the dosing date to event will be provided. In addition, the estimated survival rate at the following time-points will be presented by dose level group:

- 3 months
- 6 months
- 1 year
- 2 years
- 5 years
- 10 years

For this analysis, the date of a participant's death is considered the time of an event. Survival status should be assessed at each visit until the participant withdraws consent or completes the study. If the participant misses a visit or withdraws for a reason other than withdrawal of consent or death, the site should contact the parent(s)/LAR(s) to ascertain if the participant is

alive. For participants who withdraw from the study, the participant should be contacted every 6 months for 5 years after administration and every year for an additional 5 years (after the 5-year follow-up through 10-years follow-up) to assess for survival. If not alive, the cause and date of death should be requested and recorded.

Participants will be censored at the last known date/time of contact.

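### Time to ≤16 hours is read daily in some children and only at visits in others; the instrument partly follows dose, so with time counted from dosing, low-dose events are dated later on average.

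*SAP*

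**What the plan says.** SAP 4.4.2.2.1 presents Kaplan-Meier plots and medians separately for low and high dose, in invasively ventilated children. The hours come straight from the daily diary under protocol v5.0 and later, and from the time-off-ventilator questionnaire before that. The event rule reads: "The first instance of time reduction reported as ≤ 16 hours per day will be considered an event". On follow-up without an event, the same section has this rule: "Participants will be censored at either Week 24 or withdrawal from study, whichever occurs first". The origin is given as "time from the study start date to event will be provided", whereas for survival SAP 4.4.2.2.8 says "Kaplan-Meier plots of time from the dosing date to event will be provided".

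Protocol 5.1.1.11.2 describes the instruments. The diary is completed every day. The questionnaire records "the amount of time the subject spent off of ventilatory support in a 24-hour period at clinic and contact visits". For "subjects in Part 1 who have already completed the Week 24 visit, a daily diary will not be completed".

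For the primary endpoint, SAP 4.3.1 averages diary entries over the week and SAP 4.3.2 models both instruments at the same weeks (1, 4, 12, 16 and 24 up to Week 24). Neither step is carried over to this endpoint.

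**The concern.** A first-reading rule dates an event no earlier than the next time someone looks. A diary child is looked at daily, while a questionnaire child may wait weeks. If the two instruments were spread evenly over the dose groups, this would blur both curves alike. They are not. Instrument follows protocol version, and protocol version partly follows dose.

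The curves are shown by dose, so part of any separation would reflect how often hours were recorded and not how fast children were weaned. The SAP plans no sensitivity analysis or footnote for this endpoint that would reveal it.

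**Working it through.** The plan gives no figure for this endpoint to reproduce. Its only sample-size figure concerns the primary endpoint and has no bearing here.

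**Which children are on which instrument**

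- *Low dose.* At the cutoff of 08 July 2020 the six original low-dose children were "all of whom are ≥ 2 years from AT132 administration" (Protocol 1.4.2). They were dosed by 08 July 2018 and, even at the end of a ±14-day window (Day 182), had passed Week 24 by about 06 January 2019. Protocol v5 is dated 01 May 2019, so all six are on the questionnaire. Five of the six were invasively ventilated.
- *A seventh low-dose child, on the diary, is inferred.* Three controls were still undosed at v8/v9 (SAP 1.2) and two were never dosed (SAP 1.3). This makes 5 of 6 invasive low-dose children on the questionnaire.
- *High dose.* There are 17 children (Protocol 1.4.2). SAP 4.3.1 puts all Part 2 children on the diary. Cohort 2 had 3 children plus 3 to 5 more, and its Week 24 data were available when v5 selected the dose. I take q = 3 to 8 of 17 on the questionnaire, hence 9 to 14 on the diary, and assume all 17 were invasively ventilated.

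**How many questionnaire readings to Week 24**

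Table 9, column (i), fixes five windows: Weeks 1, 4, 12, 16 and 24. If Weeks 2, 8 and 20 were also collected there are 8. If every week to Week 16 plus Weeks 20 and 24 were collected there are 18. The v1 to v4 schedule is not in the documents, so this is an assumed range.

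**Dating delay**

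Assume the true crossing day is uniform over Days 0 to 168 from dosing. Mean wait to the next reading = Σ(gap²/2)/168 = Σ(gap²)/336.

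- 5 readings, gaps 7, 21, 56, 28, 56: (49 + 441 + 3136 + 784 + 3136)/336 = 22.46 days
- 8 readings, gaps 7, 7, 14 and five of 28: (49 + 49 + 196 + 3920)/336 = 12.54 days
- 18 readings, sixteen gaps of 7 and two of 28: (784 + 1568)/336 = 7.00 days
- Daily diary: 168/336 = 0.50 days

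For a single child with five readings the delay can reach 55 days: a first day at 16 hours or less on Day 29 is dated Day 84.

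**Gap between dose groups with identical weaning**

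Gap = (5/6 − q/17) × net delay. The multiplier is 0.363 for q = 8 and 0.657 for q = 3.

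| Readings | Net of diary (days) | Gap, q = 8 | Gap, q = 3 |
|---|---|---|---|
| 5 | 21.96 | 7.97 | 14.42 |
| 8 | 12.04 | 4.37 | 7.91 |
| 18 | 6.50 | 2.36 | 4.27 |

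The sign reverses only if at least 15 of the 17 high-dose children were on the questionnaire (15/17 = 0.88 exceeds 5/6 = 0.83; 14/17 = 0.82 does not).

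**Check with a different weaning course**

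Simulated courses (baseline 20 to 24 h, weaning onset Days 14 to 84, Week 24 reduction Normal with mean 13 and SD 6, no day-to-day variation) give a low-minus-high gap in restricted mean time to Day 168 of about 4 to 13 days for 5 to 8 readings. The medians tie at Day 112.

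**Time origin**

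Protocol 3.7 defines the study start date as the first participant's consent. The original low-dose children were dosed by 08 July 2018; Part 2 children were dosed under v5, so not before 01 May 2019. That is at least 297 days later. Read literally, the origin adds this to Part 2 event times, in the opposite direction to the reading-frequency bias and far larger than it.

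**The case against.** The strongest reply is that little rests on this display. SAP section 2 rules out hypothesis testing, the endpoint is supportive, and ventilation hours are already shown by dose at common weeks with subject line plots (SAP 4.3.2). That stands, and it limits the harm to presentation.

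A reader might infer that the high-dose median will look faster. The calculation does not support this. Under the uniform model, half the children have crossed by Day 84 (84/168), which is itself a visit day, so the expected medians coincide. In a simulation with 6 and 17 children, the difference between sample medians showed no consistent shift and had an SD of about 35 days. What remains is displacement of the curves between visit days and a shift in mean event time.

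It is also fair that the size depends on a questionnaire schedule and a high-dose split that the documents do not give. The direction is sturdier than the size.

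Finally, interval-censored estimation would handle unequal reading frequency without discarding diary data. It is a legitimate alternative; common weeks are simpler because the SAP already defines them.

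**Conclusion.** The point holds in limited form. With time from dosing and identical weaning, the rule as written dates low-dose events later on average by about 8 to 14 days (5 questionnaire readings), 4 to 8 (8 readings) or 2 to 4 (18 readings). This rests on a uniform crossing day, 5 of 6 invasive low-dose children on the questionnaire, and 3 to 8 of 17 high-dose children on it.

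Two stronger readings are not supported. One is that high dose will look faster whatever the origin: if the SAP's stated origin is taken literally, calendar time could swamp or reverse the effect. The other is that isolated low diary days create many false early events: the documents give no day-to-day SD for ventilation hours, so no size can be put on that.

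The consequence is a misleading by-dose display of one descriptive, supportive endpoint. It should be corrected because the correction is cheap.

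**What to change.** Amend SAP 4.4.2.2.1 as follows.

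1. Count time from dosing, as SAP 4.4.2.2.8 does.
2. In the main analysis, assess the event for all children only at Weeks 1, 4, 12, 16 and 24, and date it on the scheduled day. Use the questionnaire value in its Table 9, column (i), window, or the single diary entry closest to the scheduled day. For Week 24 keep the full window, Days 141 to 182. A cutoff at Day 168 would drop permitted late visits (±14 days in Protocol 5.5), mostly in low-dose children, and so introduce a new imbalance.
3. Keep the all-readings rule as a sensitivity analysis, and footnote the number of diary and questionnaire children in each dose group.

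The cost is SAP wording and light reprogramming. Event times become coarser for diary children, with up to 56 days between assessed weeks. A late Week 24 questionnaire may also capture a crossing shortly after Day 168, so the rule removes the difference in reading frequency but does not guarantee an exactly equal reading of the two instruments.

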3.3 Selection of Study Population

3.3.1 Inclusion Criteria

Subjects must meet all of the following inclusion criteria to be eligible for participation in this study. Subjects assigned to delayed-treatment control will be evaluated to confirm the subject still meets a subset (*) of the inclusion/exclusion criteria before receiving AT132.

1. Subject has a diagnosis of XLMTM resulting from a genetically confirmed mutation in the *MTM1* gene as assessed by a Sponsor-approved testing facility.*
2. Subject is male.*
3. Subject is aged less than 5 years old at dosing.*
4. Subject requires mechanical ventilatory support:
 - Part 1: Subject requires some mechanical ventilatory support (eg, ranging from 24 hours per day fulltime mechanical ventilation, to noninvasive support such as continuous positive airway pressure [CPAP] or bilevel positive airway pressure [BiPAP] during sleeping hours).
 - Part 2: Subject requires invasive mechanical ventilatory support ranging from 20 to 24 hours per day at screening (confirmed by daytime polysomnographic study).
5. Subject requiring invasive mechanical ventilator support is fitted with or willing to be fitted with a cuffed tracheostomy tube for some respiratory assessments.*
6. Subject has ventilator maximum positive end-expiratory pressure (PEEP) < 8 cmH₂O at screening.*
7. Signed informed consent by the parent(s) or legally authorized representative (LAR) (when applicable).*
8. Subject and parent(s)/LAR(s) are willing and able to comply with study visits and study procedures.*
9. UNIQUE to France: Subject's weight is ≥ 4.8 kg.

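### Time to ≤16 h/day ventilation has no baseline condition, so an invasively ventilated child already at or below 16 h could be counted as an event without any real reduction

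*SAP*

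**What the plan says.** SAP 4.4.2.2.1 sets four rules for this endpoint.

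- Population: "This endpoint will be summarized for low dose and the high dose groups separately in the participants who require invasive ventilation".
- Data: "The number of hours of ventilator support at each collected time point for this analysis will be taken directly from the daily diary", or from the time-off-ventilator questionnaire for children treated before protocol v5.
- Event: "The first instance of time reduction reported as ≤ 16 hours per day will be considered an event".
- Censoring: "Participants will be censored at either Week 24 or withdrawal from study, whichever occurs first".

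Neither SAP 1.1.2, 4.4.2.1 or 4.4.2.2.1, nor the matching protocol text (synopsis, Section 2 and the other-secondary-endpoints paragraph of Section 7.4.2), requires a baseline above 16 h or says how to treat a child who starts at or below it.

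Protocol 3.3.1, criterion 4, differs by part. For Part 1 the wording is "Part 1: Subject requires some mechanical ventilatory support", with no minimum hours. Part 2 asks for invasive support of 20 to 24 h/day, assessed at screening. Criterion 4 is not among the asterisked criteria that delayed-treatment controls must meet again before dosing.

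**The concern.** The endpoint's name speaks of a reduction, but the event rule is an absolute threshold applied to raw readings. A child on invasive support for, say, 12 h/day before dosing satisfies it without any change. Even if the word reduction is read as requiring some fall, a move from 14 h to 13.5 h would qualify.

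An event of that kind describes the child's starting state. It raises the Kaplan-Meier curve and can bring the median forward, and with groups this small one child is visible. Descriptive summaries are all the study will now deliver (SAP Sections 2 and 4.1), so the accuracy of the description is what matters. The protocol's companion endpoint, a fall of at least 6 h, is measured from the child's own level and would have been a safeguard, but the SAP does not carry it forward.

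**Working it through.** No sample size, event count or expected curve is stated for this endpoint, so there is no figure of the plan's to reproduce. Three questions can be checked.

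**1. Can such a child be in the analysis?** Yes. Part 1 had no floor on hours. For Part 2 the 20 to 24 h requirement applies at screening and is not repeated for controls before dosing, while the control schedule (Protocol 5.7) includes weaning assessments. The exposure lies mainly, but not strictly, in Part 1.

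**2. Do the published baselines show one?** Protocol 1.4.2 describes the six original low-dose children, "which had a mean 20.5 hours (SE 2.02) of ventilation per day at baseline", five on invasive and one on non-invasive support.

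- Sum of hours = 6 × 20.5 = 123.
- Sum of squared deviations = n(n − 1) × SE² = 30 × 2.02² = 122.4. Rounding of the SE (2.015 to 2.025) gives 121.8 to 123.0.
- Largest value possible if all six lie between 16 and 24 h: three at 24, two at 16, one at 19. This gives 3 × 3.5² + 2 × 4.5² + 1.5² = 36.75 + 40.5 + 2.25 = 79.5.

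Since 79.5 is well below 121.8, at least one of the six started below 16 h.

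If exactly one did, at x hours:

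- The sum of squares is smallest when the other five are equal, and is then 1.2 × (20.5 − x)². Keeping this at or below 123.0 needs x of about 10.4 or more.
- It is largest with the other five at 24, 24, 24, 16 and 35 − x, and is then (20.5 − x)² + 57 + (14.5 − x)². At x = 12.6 this is 62.41 + 57 + 3.61 = 123.0. At 12.7 it is 121.1, already too small. At 13 it is 115.5.

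So that child's baseline was about 10.4 to 12.6 h.

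Whether he was on invasive support cannot be recovered. Each of these sets sums to 123 and fits the published SE:

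| Invasive children at or below 16 h | Five invasive baselines | Non-invasive baseline | Sum of squares |
|---|---|---|---|
| 0 | 17, 22.5, 23.5, 24, 24 | 12 | 122.0 |
| 1 | 10.5, 21, 22.5, 23, 23 | 23 | 123.0 |
| 2 | 13, 15.5, 22.5, 24, 24 | 24 | 122.0 |

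**3. What would one such child do?** Take the five known invasive low-dose children, assume no early censoring, and suppose one started at or below 16 h. As written, the event proportion by Week 24 is (1 + r)/5, where r is the number of true responders among the other four. Restricted to baselines above 16 h, it is r/4.

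| True responders r | As written | Restricted |
|---|---|---|
| 0 | 20% | 0% |
| 1 | 40% | 25% |
| 2 | 60% | 50% |
| 3 | 80% | 75% |
| 4 | 100% | 100% |

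The difference is at most 20 points. If one further low-dose child were on invasive support, each affected child would weigh 1/6, or 16.7 points. The documents point to such a child: three controls were still undosed at v8/v9 (Protocol 3.1), and SAP 1.3 excludes two undosed controls.

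**The case against.** The strongest reply is that no affected child is shown to exist. The endpoint already excludes non-invasive support, and Protocol 3.3.1 gives CPAP or BiPAP during sleep as its example of the low end of Part 1 support. The low-dose child below 16 h may well be the one on non-invasive support, in which case nothing changes. This stands: the number affected may be zero.

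A second reply is that the event sentence itself speaks of a reduction, so a child with no fall has no event on the plain words. That is a fair reading of intent. But no text turns it into a comparison with baseline, and hours are taken straight from the diary or questionnaire.

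Third, the consequence is limited. This is a supportive endpoint with no hypothesis test. Baseline hours and ventilator type are summarised (SAP 4.2.4), and each child's hours are plotted (SAP 4.3.2), so an attentive reader could spot the problem. This also stands, and it keeps the point minor.

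A reader might infer more than the documents support in two respects:

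- **That only Part 1 children are exposed and one dose group is therefore favoured.** Criterion 4 is not re-checked in controls, both dose levels were given in Part 1, and high-dose baselines are not reported. Neither the size nor the direction of any imbalance can be derived.
- **That the spurious event falls in the first days after dosing.** The SAP's clock is different ("Kaplan-Meier plots along with median (95% CI) time from the study start date to event will be provided"), and the rule is not limited to post-dose readings, although diary collection starts after consent (Protocol 5.1.1.11.2.1). The timing cannot be stated.

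**Conclusion.** The gap in the rule is real. An invasively ventilated child already at or below 16 h before dosing could be counted as an event with no real reduction, and nothing elsewhere in the protocol or SAP prevents it.

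The practical effect is between nothing and a visible distortion. It is nil if every invasively ventilated child started above 16 h. Otherwise it is up to 20 percentage points per affected child among the five known invasive low-dose children. The high-dose effect cannot be sized.

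The baseline inference assumes hours between 0 and 24, an SE equal to SD/√6 and a mean of exactly 20.5. It also uses figures from the July 2020 data cut; SAP v3.0 later revised the baseline definition, so the analysis values may differ somewhat. The Week 24 comparison assumes no early censoring. No error rate or power statement is involved.

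**What to change.** Amend SAP 4.4.2.2.1 to:

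- include only participants on invasive ventilation at baseline whose baseline hours, as defined in SAP 4.3.1, exceed 16;
- count only post-dose readings as events;
- list the children excluded by the 16 h condition, by dose group, with their baseline hours.

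The cost is a sentence or two and a filter on a variable already derived for the primary endpoint. No new data are needed. The downside is a denominator smaller by possibly one or a few children, none of whom could show a fall from above 16 h. If no child is affected by the baseline condition, it changes no results. If tables from the first database lock already exist, the same restriction can be applied in the final report and the change noted there.
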